**Table 6-3 Dosing guidelines for everolimus-related hematologic toxicities**

Toxicity	Action
Grade 2 thrombocytopenia (platelets $<$ 75, $\geq$ 50x10  /L)	No action

Grade 3 thrombocytopenia (platelets <50, $\geq 25 \times 10^9/L$ )	Interrupt everolimus until resolution to grade $\leq 1$ If resolution occurs $\leq 7$ days, reintroduce everolimus at the dose level prior to interruption. If resolution occurs $> 7$ days and $\leq 28$ days, reintroduce everolimus at one dose level lower, if available.
Grade 4 thrombocytopenia (platelets < 25 $\times 10^9/L$ )	Interrupt everolimus until recovery to grade $\leq 1$ . Then reintroduce everolimus at one dose level lower, if available.
Grade 3 neutropenia or anemia (neutrophil <1, $\geq 0.5 \times 10^9/L$ )	Interrupt everolimus until resolution to grade $\leq 1$ or baseline value If AE resolution occurs $\leq 7$ days, reintroduce everolimus at the same dose level. If AE resolution occurs $> 7$ days and $\leq 28$ days, reintroduce everolimus at one dose level lower, if available.
Grade 4 neutropenia or anemia	Interrupt everolimus until recovery to grade $\leq 1$ or baseline value. Reintroduce everolimus at one dose level lower, if available.*
Febrile neutropenia	Interrupt everolimus until resolution to grade $\leq 1$ (or baseline value) and no fever. Reintroduce everolimus at one dose level lower, if available.*
Recurrence of grade 3 toxicity after dose reduction	Reduce dose to the next lower dose level, if available. The lowest possible dose level of everolimus is 5 mg every other day (2.5 mg daily). Below this level, everolimus must be discontinued.
*Recurrence of grade 4 toxicity (including febrile neutropenia) after dose reduction	Discontinue everolimus
*Any hematologic toxicity requiring Everolimus interruption for > 28 days	Discontinue everolimus

Overall, safety data available from completed, controlled and uncontrolled studies indicate that everolimus is generally well tolerated at weekly or daily dose schedules. The safety profile is characterized by manageable adverse events (AEs). These AEs are generally reversible and non-cumulative.

Adverse events most frequently observed with everolimus are stomatitis, rash, diarrhea, fatigue, infections, asthenia, nausea, peripheral edema, decreased appetite, headache, dysgeusia, epistaxis, mucosal inflammation, pneumonitis, weight decreased, vomiting, pruritus, cough, dyspnea, dry skin, nail disorder, and pyrexia. Overall, the most frequently observed laboratory abnormalities include decreased hematologic parameters including hemoglobin, lymphocytes, platelets, and neutrophils (or collectively as pancytopenia); increased clinical chemistry parameters including cholesterol, triglycerides, glucose, aspartate transaminases, creatinine, alanine transaminases, and bilirubin; and decreased clinical chemistry parameters including phosphate and potassium. The majority of these AEs have been of mild to moderate severity (NCI CTC grade 1-2).

### 6.2.2.1 Management of infections

Everolimus has immunosuppressive properties and may predispose patients to bacterial, fungal, viral or protozoal infections, including infections with opportunistic pathogens. Localized and systemic infections, including pneumonia, other bacterial infections, invasive fungal infections,

such as aspergillosis or candidiasis and viral infections including reactivation of hepatitis B virus, have been described in patients taking everolimus. Some of these infections have been severe (e.g. leading to respiratory or hepatic failure) and occasionally have had a fatal outcome.

Physicians and patients should be aware of the increased risk of infection with everolimus. Treat pre-existing infections prior to starting treatment with everolimus. While taking everolimus, be vigilant for symptoms and signs of infection; if a diagnosis of infection is made, institute appropriate treatment promptly and consider interruption or discontinuation of everolimus.

If a diagnosis of invasive systemic fungal infection is made, discontinue everolimus and treat with appropriate antifungal therapy.

### 6.2.2.2 Management of skin toxicity

For patients with grade 1 toxicity, no specific supportive care is usually needed or indicated. Rash must be reported as an AE. Patients with grade 2 or higher toxicity may be treated with the following suggested supportive measures at the discretion of the investigator: oral minocycline, topical tetracycline, topical clindamycin, topical silver sulfadiazine, diphenhydramine, oral prednisolone (short course), topical corticosteroids, or pimecrolimus.

### 6.2.2.3 Management of stomatitis / oral mucositis / mouth ulcers

**Table 6-4: Management of stomatitis/oral mucositis/mouth ulcers**

Adverse Drug Reaction	Severity	Afinitor Dose Adjustment and Management Recommendations
Stomatitis	Grade 1	No dose adjustment required. Manage with non-alcoholic or salt water (0.9%) mouth wash severaltimes a day.
	Grade 2	Temporary dose interruption until recovery to grade $\leq 1$ . Re-initiate everolimus at same dose. If stomatitis recurs at grade 2, interrupt dose until recovery to grade $\leq 1$ . Re-initiate everolimus at lower dose. Manage with topical analgesic mouth treatments (e.g. benzocaine, butyl aminobenzoate, tetracaine hydrochloride, methol or phenol) with or without topical corticosteroids (i.e. triamcinolone oral paste)*.
	Grade 3	Temporary dose interruption until recovery to grade $\leq 1$ . Re-initiate everolimus at lower dose. Manage with topical analgesic mouth treatments (i.e. benzocaine, butyl aminobenzoate, tetracaine hydrochloride, methol or phenol) with or without topical corticosteroids (i.e. triamcinolone oral paste)*
	Grade 4	Discontinue everolimus and treat with appropriate medical therapy.

\* **Avoid** using agents containing hydrogen peroxide, iodine, and thyme derivatives in management of stomatitis as they may worsen mouth ulcers.

Patients with a clinical history of stomatitis/mucositis/mouth ulcers and those with gastrointestinal morbidity associated with mouth/dental infections, irritation of esophageal

mucosa e.g. gastroesophageal reflux disease (GERD) and pre-existing stomatitis/mucositis must be monitored even more closely. Patients should be instructed to report the first onset of buccal mucosa irritation/reddening to their study physician immediately.

Stomatitis/oral mucositis/mouth ulcers due to everolimus should be treated using local supportive care. Please note that investigators in earlier trials have described the oral toxicities associated with everolimus as mouth ulcers, rather than mucositis or stomatitis. If your examination reveals mouth ulcers rather than a more general inflammation of the mouth, please classify the adverse event as such. The suggested paradigm for treatment of stomatitis/oral mucositis/mouth ulcers is as follows:

1. For mild toxicity (grade 1), no dose adjustment required. Manage with non-alcoholic mouth wash or salt water (0.9%) mouth wash several times a day until resolution.
2. For more severe toxicity (grade 2 in which case patients have pain but are able to maintain adequate oral alimentation, or grade 3 in which case patients cannot maintain adequate oral alimentation), the suggested treatments are topical analgesic mouth treatments (i.e., local anesthetics such as, benzocaine, butyl aminobenzoate, tetracaine hydrochloride, menthol, or phenol) with or without topical corticosteroids, such as triamcinolone oral paste 0.1% (Kenalog in Orabase®).
3. Agents containing alcohol, hydrogen peroxide, iodine, and thyme derivatives may tend to worsen mouth ulcers. These agents should be avoided.
4. Antifungal agents should be avoided unless a fungal infection is diagnosed. In particular, systemic imidazole antifungal agents (ketoconazole, fluconazole, itraconazole, etc.) should be avoided in all patients due to their strong inhibition of everolimus metabolism, therefore leading to higher everolimus exposures. Therefore, topical antifungal agents are preferred if an infection is diagnosed.

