**Table 6-2 Dosing guidelines for Everolimus-related non-hematologic toxicities**

Toxicity	Action
Non-Infectious Pneumonitis	Please refer to Table 6-6 .
AST or ALT elevation Grade 1 (> ULN - 3.0 x ULN) Grade 2 (> 3.0 - 5.0 x ULN)	Maintain current dose level
AST or ALT elevation Grade 3 (> 5.0 - 20.0 ULN)*	Interrupt everolimus administration until resolution to $\leq$ grade 1 (or $\leq$ grade 2 if baseline values were within the range of grade 2). If resolution occurs $\leq$ 7 days, everolimus should be re-started at the dose level prior to interruption. If resolution takes $>$ 7 days, or if event recurs within 28 days, hold everolimus until recovery to $\leq$ grade 1 or baseline grade / value and reintroduce everolimus at one dose level lower, if available.
AST or ALT elevation Grade 4 (> 20 x ULN)*	Interrupt everolimus administration until resolution to $\leq$ grade 1 (or $\leq$ grade 2 if baseline values were within the range of grade 2). If resolution occurs $\leq$ 7 days, everolimus should be re-started at one dose level lower. If resolution takes $>$ 7 days, discontinue everolimus. Discontinue everolimus.
Recurrence of grade 4 after dose reduction or toxicity requiring Everolimus interruption for $>$ 28 days	
Intolerable grade 2 mucositis, or grade 3 AE, except hyperglycemia or hypertriglyceridemia or hypercholesterolemia (see Section 6.2.2.5 )	Interrupt everolimus administration until resolution to $\leq$ grade 1 or baseline grade / value. If resolution occurs within $\leq$ 7 days, everolimus should be re-started at the dose level prior to interruption. If resolution takes $>$ 7 days, or if event recurs within 28 days, hold everolimus until recovery to $\leq$ grade 1 or baseline grade / value and reintroduce everolimus at one dose level lower, if available. Patients will be withdrawn from the study if they fail to recover to $\leq$ grade 1 or baseline grade / value within 28 days.
Any other grade 4	Hold everolimus until recovery to grade $\leq$ 1 or baseline value Reintroduce everolimus at one dose level lower, if available.
Grade 3 or 4 clinical liver failure (asterixis or encephalopathy/coma)	Discontinue everolimus
Recurrence of intolerable grade 2 mucositis or grade 3 event after dose reduction	Reduce dose to the next lower dose level, if available. The lowest possible dose level of everolimus is 2.5 mg daily. Below this level, everolimus must be discontinued.

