## 9.4 Stopping Rules

If the discontinuation rate due to toxicity is 20% or greater and the lower bound for the one-tailed 95% confidence interval is > 10%, this strategy would not be considered feasible. Six months after the 20th patient is enrolled and six months after the 40th patient is enrolled, we will assess the frequency of toxicity requiring permanent discontinuation of the drug. If there is a greater than 20% rate for discontinuation of drug due to toxicity during therapy at either time point, the study accrual will be suspended and we will assess the study design. Because the confidence interval may be calculated multiple times, the actual confidence level will be overstated. This increases the likelihood of rejecting the therapy due to toxicity. However, this is felt to be an acceptable risk in order to prevent continuation of a therapy that may have a toxicity rate that precludes its routine use.

If there is any treatment-related mortality event, the study accrual will be suspended until all data pertaining to the event is reviewed by the Study Chair and co-investigators.

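### Tables 6-2 and 6-4 direct different everolimus actions for some grade 2, 3 and 4 mouth toxicity and no text says which governs; at grade 4 this bears on the Section 9.4 discontinuation count

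*Combined protocol and SAP*

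**What the plan says.** Section 6.2.2 introduces Tables 6-2 and 6-3 as the dosing guidelines for everolimus toxicity. One row of Table 6-2 covers "Intolerable grade 2 mucositis, or grade 3 AE, except hyperglycemia or hypertriglyceridemia or hypercholesterolemia" and then points to Section 6.2.2.5. If such an event resolves within 7 days, "everolimus should be re-started at the dose level prior to interruption". If it takes longer, or recurs within 28 days, the instruction is to hold and then "reintroduce everolimus at one dose level lower, if available". A separate catch-all row for other grade 4 events holds the drug until recovery and then gives the same one-level reduction. Further rows discontinue everolimus if grade 4 recurs after a dose reduction, or if a non-hematologic interruption exceeds 28 days.

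Table 6-4, in Section 6.2.2.3, has its own dose-adjustment column for stomatitis. A first grade 2 episode is interrupted and restarted at the same dose. For grade 3, after interruption, the row reads "Re-initiate everolimus at lower dose. Manage with topical analgesic mouth treatments (i.e. benzocaine" and goes on with local treatments; it sets no condition on time to resolution. For grade 4 it reads "Discontinue everolimus and treat with appropriate medical therapy". Table 6-5, in Section 6.2.2.5, gives the same grade 4 instruction for metabolic events.

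Section 9.4 says that six months after the 20th and the 40th patient is enrolled, "we will assess the frequency of toxicity requiring permanent discontinuation of the drug". A rate above 20% at either time suspends accrual.

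**The concern.** An investigator facing a severe mouth toxicity can open two tables in the same section and find two instructions. At grade 4, one ends everolimus and the other continues it at a lower level. That is a matter of patient safety and of consistent handling.

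It also reaches the statistics. The rate-based trigger in Section 9.4 counts permanent discontinuations for toxicity. If the table consulted determines whether a patient stops for good, the count reflects that choice as well as the tolerability of the drug. The grade 2 and grade 3 differences change the restart dose. They reach the count only indirectly, because a dose level used up earlier leaves fewer before everolimus must be stopped.

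**Working it through.** The plan states no figure on this point, so there is none to reproduce. The check sets the rows side by side and then asks what one patient does to the Section 9.4 rule.

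**Step 1. The rows compared**

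| Event | Table 6-2 | Table 6-4 or 6-5 | Where they diverge |
|---|---|---|---|
| Grade 4 stomatitis | Hold, then one level lower | Discontinue (6-4) | First event, recovery within 28 days, lower level available |
| Grade 3 stomatitis | Prior dose if resolved in 7 days or less; otherwise one level lower | Lower dose in every case (6-4) | Resolution in 7 days or less, no recurrence within 28 days |
| Intolerable grade 2 mucositis, first episode | One level lower if resolution takes more than 7 days | Same dose (6-4) | Resolution in more than 7 days |
| Grade 4 metabolic event | Hold, then one level lower, on the literal text | Discontinue (6-5) | As for grade 4 stomatitis, unless the grade 3 pointer is read to extend to grade 4 |

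Outside the last column the tables agree or nearly agree. For example, both lower the dose for grade 3 stomatitis that is slow to resolve.

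**Step 2. Is there a precedence rule?** None was found. Table 6-2 redirects in two places: pneumonitis goes to Table 6-6, and the metabolic exception goes to Section 6.2.2.5. The metabolic exception is written only in the grade 3 row. No row sends stomatitis to Table 6-4, and Table 6-2 names mucositis in its own rows.

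**Step 3. The Section 9.4 boundary.** Take the looks as covering the first 20 and first 40 patients pooled over arms (an assumption; the section gives no denominator by arm). Since 0.20 × 20 = 4 and 0.20 × 40 = 8, a rate above 20% means 5 or more of 20, or 9 or more of 40. The exact one-sided 95% lower bound is L = Beta⁻¹(0.05; x, n − x + 1):

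- 4/20 = 20.0%, L = 7.1%: no suspension
- 5/20 = 25.0%, L = 10.4%: suspension
- 8/40 = 20.0%, L = 10.4%: no suspension
- 9/40 = 22.5%, L = 12.3%: suspension

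The suspension trigger uses only the rate. The bounds belong to the separate feasibility sentence (rate 20% or more and lower bound above 10%). At either boundary, one patient classified differently changes the outcome.

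**Step 4. Dependence on an unknown rate.** Let f be the share of patients who have a grade 4 event on which the tables diverge and who would not otherwise stop for toxicity. The discontinuation rate under Tables 6-4 and 6-5 is then the rate under Table 6-2 plus f. The documents do not give f. For a true rate p, with independent patients, the chance of triggering at either look is

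P(X ≥ 5) + Σ (x = 0 to 4) P(X = x) · P(Y ≥ 9 − x), with X and Y each Binomial(20, p).

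This gives 5.0% at p = 10%, 11.8% at 12.5%, 22.3% at 15%, 35.8% at 17.5% and 50.5% at 20%. From an assumed 15%, the chance stays at 22.3% if f = 0, rises to 35.8% if f is 2.5 points (one patient in 40) and to 50.5% if f is 5 points (one in 20). These are conditional illustrations; nothing in the protocol supports any particular f.

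**The case against.** The strongest reply is that the specific table overrides the general one, and that a row for other grade 4 events means those with no table of their own. Many clinicians would read it so. It carries real weight for metabolic events, because Table 6-2 already names them and points to the section holding Table 6-5; that limb is therefore the weaker one. It carries less for stomatitis: no pointer exists, and Table 6-2 itself gives dosing for mucositis.

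Second, the grade 4 gap is narrow. Table 6-2 also discontinues after a recurrence following dose reduction or an interruption beyond 28 days, and Section 8.3 allows re-challenge after some stopped treatments. This stands, and it confines the conflict to the cases in Step 1.

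Third, a reader might infer that the stopping rule is likely to be tripped by this ambiguity, since stomatitis and metabolic changes are listed among the most frequent events and raised laboratory values. The documents do not support that. Section 6.2.2 adds that most of these events were grade 1-2, and no grade 4 rate is given. Any single event at 4/20 would tip the rule, so that example does not measure this defect.

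Fourth, a reader might take discontinuation to be all that Section 9.4 watches. It is not: any treatment-related death also suspends accrual. Nor does crossing the 20% rate end the trial; accrual is suspended and the design assessed.

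Finally, the primary analysis is by intention to treat, and PFS counts events whether or not drug was stopped (Sections 9.1 and 9.5). How the primary endpoint is counted is therefore unaffected.

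**Conclusion.** The protocol contradicts itself as written. The clearest conflict is a first grade 4 stomatitis recovering within 28 days, where one table continues everolimus and the other ends it. The grade 3 and grade 2 conflicts are real but limited to the restart dose in the circumstances shown. The grade 4 metabolic conflict holds on the literal text and is softer.

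For the statistics, the grade 4 conflicts bear directly on who is counted in the rate-based trigger of Section 9.4, where the margin at either boundary is one patient. How often that would matter cannot be stated, because the grade 4 rate is unknown and may be small. The point rests on the text of the tables and the absence of a precedence sentence. The figures in Steps 3 and 4 rest on pooled looks at exactly 20 and 40 patients; Step 4 also assumes rates that the documents do not give.

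**What to change.** Reconcile Tables 6-2, 6-4 and 6-5 so that each event and grade has one action, or add a sentence stating which table takes precedence. If the event-specific tables are meant to govern, Table 6-2 needs a pointer for stomatitis and a metabolic exception that reaches its grade 4 row. If Table 6-2 is meant to govern, the dose columns of the other tables need aligning with it. In the same pass, settle whether interruption at grade 2 applies to all stomatitis (Table 6-4) or only to intolerable mucositis (Table 6-2).

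Which action is right is for the sponsor's clinicians, and none is proposed here. The cost is an amendment to wording. Sample size, endpoints and assessments do not change. If patients have already been treated under the present text, record which table was followed for each affected event, so that the Section 9.4 count can be interpreted.

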#### **6.2.2.4 Management of diarrhea**

Appearance of grade 1-2 diarrhea attributed to study drug toxicity may be treated with supportive care such as loperamide, initiated at the earliest onset (for example 4 mg orally followed by 2 mg orally every 2 hours until resolution of diarrhea).

#### **6.2.2.5 Management of hyperlipidemia and hyperglycemia**

**Table 6-5: Management of hyperlipidemia and hyperglycemia**

Adverse Drug Reaction	Severity	Everolimus Dose Adjustment and Management Recommendations
Metabolic events (e.g. hyperglycemia, dyslipidemia)	Grade 1	No dose adjustment required. Initiate appropriate medical therapy and monitor.
	Grade 2	No dose adjustment required. Manage with appropriate medical therapy and monitor.
	Grade 3	Interrupt everolimus administration until resolution to $\leq$ grade 1 (or $\leq$ grade 2 if baseline values were within the range of grade 2). Re-initiate everolimus at lower dose. Manage with appropriate medical therapy and monitor.
	Grade 4	Discontinue everolimus and treat with appropriate medical therapy.

Treatment of hyperlipidemia should take into account the pre-treatment status and dietary habits of the patient. Grade 2 or higher hypercholesterolemia ( $>300$  mg/dL or 7.75 mmol/L) or grade 2 hypertriglyceridemia or higher ( $>2.5$  times upper normal limit) should be treated with a 3-hydroxy-3-methyl-glutaryl (HMG)-CoA reductase inhibitor (e.g. atorvastatin, pravastatin, fluvastatin) or appropriate triglyceride-lowering medication, in addition to diet.

Note: Concomitant therapy with fibrates and an HMG-CoA reductase inhibitor is associated with an increased risk of a rare but serious skeletal muscle toxicity manifested by rhabdomyolysis, markedly elevated creatine phosphokinase (CPK) levels and myoglobinuria, acute renal failure and sometimes death. The risk versus benefit of using this therapy should be determined for individual patients based on their risk of cardiovascular complications of hyperlipidemia.

Hyperglycemia has been reported in clinical trials. Monitoring of fasting serum glucose is recommended prior to the start of everolimus and periodically thereafter. Optimal glycemic control should be achieved before starting a patient on everolimus.

#### **6.2.2.6 Management of non-infectious pneumonitis**

Non-infectious pneumonitis is a class effect of rapamycin derivatives. Cases of non-infectious pneumonitis (including interstitial lung disease) have also been described in patients taking everolimus. Some of these have been severe and on rare occasions, a fatal outcome was observed.

- A diagnosis of non-infectious pneumonitis should be considered in patients presenting with non-specific respiratory signs and symptoms such as hypoxia, pleural effusion, cough or dyspnea, and in whom infectious, neoplastic and other non-medicinal causes have been excluded by means of appropriate investigations. Patients should be advised to report promptly any new or worsening respiratory symptoms.

- Patients who develop radiological changes suggestive of non-infectious pneumonitis and have few or no symptoms may continue everolimus therapy without dose alteration. If symptoms are moderate (grade 2), consideration should be given to interruption of therapy until symptoms improve. The use of corticosteroids may be indicated. Everolimus may be reintroduced at a daily dose approximately 50% lower than the dose previously administered.
- For cases where symptoms of non-infectious pneumonitis are severe (grade 3 or 4), everolimus therapy should be discontinued and the use of corticosteroids may be indicated until clinical symptoms resolve. For cases of grade 3 non-infectious pneumonitis, Therapy therapy with everolimus may be re-initiated at a daily dose approximately 50% lower than the dose previously administered depending on individual clinical circumstances

If non-infectious pneumonitis develops, the guidelines in [Table 6-6](#) should be followed. Consultation with a pulmonologist is recommended for any case of pneumonitis that develops during the study.

